## Revision History

Version Number: 1

Version Date: 12/7/18

Version Number: 2

Version Date: 3/22/18

**Summary of Revisions Made:** A detailed procedure for monitoring and recording adverse events and severe adverse events was added. The number of assessment visits for each time point (baseline and post assessment) has been changed from 2 to 1. The protocol was revised so that the CDI will be administered at screening so that all eligibility criteria are met by participants prior to starting the baseline assessment. The protocol also now states that the PI of the study will be blind to group assignment and [name] will provide clinical supervision. A table about blinding and additional explanatory text was added. The randomization procedures were changed. Lastly, measures including the adverse event query form, menstruation query form, Parent Pain Visual Analog Scale, and Concomitant Medications Form were added to the table of events and the Anxiety Diagnostic Interview Schedule was removed.

Version Number: 3

Version Date: 4/30/18

**Summary of Revisions Made:** The protocol was revised so that the Functional Disability Inventory (FDI) and Visual Analog Scale for Pain Intensity (VAS) will be administered at the screening visit in addition to the baseline and post assessment visits. Additional eligibility requirements were included in the inclusion criteria including at least moderate disability (FDI  $\geq$  8) and a highest reported pain of at least 3/10 in the past 2 weeks according to the VAS. Additionally, participants and their parents will have the option to complete baseline and follow up assessment measures at home prior to their scheduled visit using their own electronic devices. We will provide them with a RedCap link to the measures via email within a few days of their scheduled visit. This option would reduce the length of the in-person assessment visits and thus reduce participant burden. If participants do not choose to complete measures prior to their visit, they will be administered during the assessment visit. Text detailing this was added to the protocol. The number of participants we plan to approach was also adjusted for accuracy.

Version Number: 4

Version Date: 5/15/18

**Summary of Revisions Made:** The protocol reformatted to comply with the NCCIH protocol guidelines.

Version Number: 5

Version Date: 8/15/18

**Summary of Revisions Made:** The screening procedures were amended such that in circumstances in which the FDI, SCARED, or Numeric Rating Scale (NRS) are unavailable in

EPIC, any participant approached will be consented and administered all three measures. We have noted that if the scores from the three measures indicate study ineligibility, the remaining screening measures will not be given. Moreover, the protocol now allows for anyone interested in the study who was unable to meet in-person with study staff during their outpatient visit to set up a screening appointment outside of an office visit. FAPD will be confirmed with the provider using the EMR and/or direct communication with the provider. Abdominal migraine was added to the description of the Rome IV FAPD Diagnosis Checklist. The explanation of the water load symptom provocation task (WL-SPT) was revised to state that the WL-SPT has been used in adult studies. The protocol now states that the Adverse Event Query Form will be administered during ADAPT session 2 and post-assessment for participants randomized to the ADAPT treatment group. The protocol was also revised to explain that participants randomized to the waitlist will receive the Adverse Event Query Form at post-assessment, and if they choose to participate in ADAPT after the waitlist period, they will receive the Query during ADAPT session 2 and over the phone after ADAPT session 6. We have clarified that the Numeric Rating Scale (NRS) will be used for screening, while the baseline and post-assessments will primarily use the Visual Analog Scale (VAS). If the VAS cannot be obtained because of technical difficulties with the slider, we will use the NRS instead. The protocol now explains that we will allow up to 8 weeks to complete ADAPT, rather than 6 weeks. Several typographical errors were corrected, including in sections 6.2.3, 6.2.4, 7.2, 7.3, and 11.2. We also updated the Menstruation Query, Concomitant Medications, and Baseline/Post Demographic Information forms to include clarifying questions and language. For the Baseline/Post Demographic Information Forms under the "School Information" section, "Not Applicable" responses were added to increase clarity. The Menstruation Query for baseline and post assessment were revised to include a question about current pain levels due to menstruation. The FDI-Child and FDI-Parent Forms had item 8 modified to increase clarity for participants and caregivers whose children are not currently in school. The fMRI Pain and Anxiety Ratings Form was updated to add a clarifying "not applicable" option to an item along with a notes section to explain any unusual circumstances such as the need to conduct a fMRI rescan due to significant participant movement. Updated version numbers were added to revised measures. An "Other Pain" measure was added to assess alternative pain sources and better contextualize imaging data. This measure will be administered during baseline and post assessment. The Contact Information form was modified to allow for more clarifying information. The Adverse Event Query, Adverse Event Detail, and Serious Adverse Event forms have also been updated to reflect more accurate administration time points (ADAPT Sessions 2 and 6, Post Assessment).

## PRÉCIS

### Study Title

Using fMRI to understand response to an integrative treatment for pain and anxiety in pediatric functional abdominal pain disorders (FAPD).

### Objectives

**Aim 1.** Left AMY-PFC functional connectivity will be significantly diminished (i.e., evidence of decreased hyperconnectivity) during the water load symptom provocation task (WL-SPT) post ADAPT vs. waitlist.

**Aim 2.** Brain activations associated with cognitive (PFC), affective (pgACC, AMY), and visceral afferent (INS, thalamus, aMCC, S1 & S2) pain will significantly be more diminished after ADAPT vs. waitlist.

*Exploratory Aim.* Changes in functional connectivity and brain activations following ADAPT will correspond to reductions in pain (intensity and unpleasantness) and anxiety ratings.

[figure not shown]
### Design and Outcomes

In this study, brain mechanisms implicated in the modulation of pain during a symptom provocation task in relation to response to a psychological intervention for pediatric FAPD will be investigated. Participants with FAPD and comorbid anxiety will complete a screening to assess eligibility. Next, they will complete a baseline assessment where they will undergo an fMRI to explore changes in functional connectivity during visceral pain induction (via the water load symptom provocation task; WL-SPT). Participants will then be randomized to either ADAPT or waitlist control. A post assessment will be conducted approximately 6 weeks later where participants will again undergo an fMRI and complete the WL-SPT. Changes in functional connectivity and brain activations will be observed and compared for participants in each treatment condition (ADAPT intervention or waitlist control).

It is expected that Left AMY-PFC functional connectivity will be significantly diminished (i.e., show evidence of decreased hyperconnectivity) during the WL-SPT post ADAPT vs. waitlist (Aim 1). In addition (Aim 2), brain activations associated with cognitive (PFC), affective (pgACC, AMY), and visceral afferent (INS, thalamus, aMCC, S1 & S2) pain will significantly be more diminished after ADAPT vs. waitlist. Finally, we predict changes in functional connectivity and brain activations following ADAPT will correspond to reductions in pain (intensity and unpleasantness) and anxiety ratings (exploratory Aim).

Conventional blood oxygenation level dependent (BOLD) fMRI will be used to assess functional connectivity to capture moment-to-moment fluctuations in activity (Aim 1). In Aim 2, changes in regional brain activation for those receiving ADAPT will be compared to those in the waitlist condition. The novel arterial spin label (ASL) MRI technique will be used to gain inferences into regional brain activity since these activations represent a relatively steady-state. In line with the NCCIH funding priorities, this study seeks to increase understanding of the mechanisms through which mind and body approaches impact clinical outcomes in chronic pain and

anxiety. Results will advance the field by providing crucial information needed for the refinement and testing of a tailored mind body intervention for FAPD and comorbid anxiety.

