## 2.2 Study Rationale

Given this research evidence, Aim to Decrease Pain and Anxiety Treatment (ADAPT) was developed. ADAPT is a cognitive behavioral approach to manage pain and anxiety for youth with FAPD and comorbid anxiety. For the current study, ADAPT is enhanced with mindfulness meditation. Thus, ADAPT focuses on decreasing attention to pain and anxiety using conventional strategies (CBT), as well as training in mindfulness meditation techniques, such as mindful breathing, developing a mindful awareness of bodily sensations, recognizing the impact of stress on functioning. ADAPT utilizes a blend of 2 interactive sessions with a psychological provider (1 hour, via videoconference) and 4 web-based, self-paced modules (45 minutes) with therapist support videoconferencing and/or phone calls (15 minutes). The Zoom-based ADAPT sessions will be video-recorded. The ADAPT intervention period is approximately 6 weeks (up to eight weeks will be allowed for scheduling flexibility). Based on our prior research, there are no known risks associated with the ADAPT intervention.

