## 9. STATISTICAL CONSIDERATIONS

### 9.1 General Design Issues

The statistical hypotheses:

**Aim 1.** Left AMY-PFC functional connectivity will be significantly diminished (i.e., evidence of decreased hyperconnectivity) during the water load symptom provocation task (WL-SPT) post ADAPT vs. waitlist.

**Aim 2.** Brain activations associated with cognitive (PFC), affective (pgACC, AMY), and visceral afferent (INS, thalamus, aMCC, S1 & S2) pain will significantly be more diminished after ADAPT vs. waitlist.

*Exploratory Aim.* Changes in functional connectivity and brain activations following ADAPT will correspond to reductions in pain (intensity and unpleasantness) and anxiety ratings.

The choice of study design (blinded clinical trial) will enable us to answer these research questions.

Primary and secondary outcome measures are obtained from neuroimaging data. The brain regions selected have been shown in prior literature to be related to chronic pain and response to psychological interventions for the management of chronic pain conditions.

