### **9.5.2 Secondary Outcomes**

Brain activation during the WL-SPT will be assessed by arterial spin labeling (ASL). In order to examine relationships between resting brain activity and other variables, cerebral blood flow (CBF) will be measured in a quantitative fashion via ASL, which is the optimal for assessing steady-state conditions. Nine series will be obtained (5-10 mins each): Pre-WL-SPT: 1 MPRAGE; 2 resting ASLs; 2 resting BOLDs; post-WL-SPT: 2 ASLs; and 2 BOLDs.

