## **9.6 Data Analyses**

For fMRI analysis, image processing and data analysis will be accomplished by FSL software. Each subject's functional images will be registered to their structural data using a six-parameter linear 3D transformation and then nonlinearly warped to standard space (MNI152). Analyses of both BOLD and ASL data will be accomplished via mixed effects ANOVAs. Data will be coded prior to analysis to conceal patient status to ensure blinding.

Clusters of activation will be identified using a threshold of  $Z > 3.1$  and statistical significance will be estimated according to Gaussian random field theory. Functional connectivity analysis will be conducted (Aim 1) to identify changes in functional connectivity between the AMY-PFC in ADAPT completers vs. those in the waitlist condition. A seed to whole brain analytic approach will be used to identify any/all differences observed. Pain-related brain activations are expected to diminish for those that complete ADAPT compared to the waitlist condition (Aim 2). For the exploratory aim, mechanisms associated with a positive treatment response (decreased pain intensity/ unpleasantness/ anxiety during WL-SPT) after ADAPT will be identified. Normalization of abnormal connectivity patterns are predicted to categorize changes in pain and anxiety. Specifically, decreases in brain activations and reductions in functional connectivity will be examined in relation to improvements in pain and anxiety post treatment using multiple (linear) regression.

While all efforts will be made to minimize missing data through the use of electronic data capture and real-time adherence data collection, missing data is still inevitable in RCTs. Thus, we will employ several strategies to handle missing data with specific attention on how to handle missing not-at-random. Specifically,

missing data will be handled via ML estimation with auxiliary correlate inclusion (e.g., Graham, 2003; Enders, 2010). Missing not at random will be addressed with mixture MNAR methods (e.g., Gottfredson, Bauer, & Baldwin, 2014; Muthen, et al., 2011; Sterba & Gottfredson, 2015).

Given that other factors such as pubertal status and subjective pain levels could influence the outcome, these factors will be included in the analysis as control covariates. Each participant's exact age will be recorded at assessment allowing personnel to control for age as an additional covariate should the need become apparent during preliminary analyses.

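### Aim 2 reads regional, pain-related change from ASL blood flow, but the plan has no whole-brain flow term and does not state the contrast, so a brain-wide fall in ADAPT could be reported as regional.

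*Combined protocol and SAP*

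**What the plan says.** The Précis (Design and Outcomes) assigns Aim 2 to arterial spin labelling: "The novel arterial spin label (ASL) MRI technique will be used to gain inferences into regional brain activity". Section 9.1 names the targets as "Brain activations associated with cognitive (PFC), affective (pgACC, AMY), and visceral afferent (INS, thalamus, aMCC, S1 & S2) pain". That is eight regions (PFC, pgACC, AMY, INS, thalamus, aMCC, S1, S2), all predicted to fall more after ADAPT.

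Section 9.5.2 refers to activation during the water load task. It then says, in a sentence about relating resting activity to other variables, that "cerebral blood flow (CBF) will be measured in a quantitative fashion via ASL, which is the optimal for assessing steady-state conditions". The series at each visit are "Pre-WL-SPT: 1 MPRAGE; 2 resting ASLs; 2 resting BOLDs; post-WL-SPT: 2 ASLs; and 2 BOLDs", so flow is measured both before and after the water load.

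Section 9.6 gives the analysis: "Analyses of both BOLD and ASL data will be accomplished via mixed effects ANOVAs". Clusters are formed at Z > 3.1 with Gaussian random field inference. The covariate sentence reads "pubertal status and subjective pain levels could influence the outcome, these factors will be included in the analysis as control covariates", and exact age may be added if preliminary analyses suggest it. Neither document section mentions global, whole-brain or mean grey-matter CBF, relative CBF, scaling or a reference region, and neither defines the Aim 2 contrast.

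**The concern.** Eight regions drawn from cognitive, affective and sensory systems, all predicted to move down, form the same pattern that a uniform fall in flow would produce. The cluster threshold guards against chance findings. It does not guard against a real shift that is not regional. If flow fell throughout the brain in ADAPT relative to waitlist, the planned model could return significant falls in named regions, and the secondary objective would be read as a regional pain mechanism. The exploratory aim relates these activation changes to improvement in pain and anxiety, so the same ambiguity would carry into it.

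A difference between arms in whole-brain flow is possible: ADAPT includes "training in mindfulness meditation techniques, such as mindful breathing" and is meant to lower anxiety, while waitlist has no comparable activity. The documents give no figure for the effect of either on CBF, so this is a reason to check and not evidence that a shift will occur.

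**Working it through.** **Plan's own figures.** Section 9.2 gives totals of 34, 35 and 40, derived from functional connectivity data with a web tool whose inputs are not shown. No figure is given for ASL or CBF, so there is nothing to reproduce for Aim 2.

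**Inputs from the documents.** Eight regions (9.1); a decrease as the predicted direction and Z > 3.1 as the threshold (9.6); a total of 40 (9.2), taken as 20 per arm.

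**Assumptions, not in the documents.** There is no region-specific effect. The between-child SD of the visit-to-visit change in global CBF is 10% (set A) or 15% (set B). The region-specific SD is 5% (A) or 8% (B). For the within-session contrast, the response to water is 10% of resting flow and a global shift acts multiplicatively. Each region is tested as a single value at the Z > 3.1 level; cluster extent is not modelled.

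**One region, raw CBF, global shift of -10%.**
- SD of regional change = √(global² + regional²). A: √(10² + 5²) = 11.2%. B: √(15² + 8²) = 17.0%.
- SE of the arm difference = SD × √(2/20). A: 3.54%. B: 5.38%.
- Shift/SE. A: 10/3.54 = 2.83. B: 10/5.38 = 1.86.
- Z > 3.1 has a one-tailed p of 0.00097, which on 38 degrees of freedom is t > 3.33. By noncentral t, the chance that a given region passes is about 33% (A) or 9% (B).

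**One region, post-minus-pre contrast, same shift.** Only 10% × 10% = 1% carries into the difference.
- A: SD √(1² + 5²) = 5.10%, SE 1.61%, ratio 0.62, chance 0.59%; for any of eight, 1 - (1 - 0.0059)⁸ = 4.6%.
- B: SD √(1.5² + 8²) = 8.14%, SE 2.57%, ratio 0.39, chance 0.31%; for any of eight, 2.5%.
- With no shift at all, any of eight: 1 - (1 - 0.00097)⁸ = 0.8%.

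**Eight regions sharing the global component (3,000 simulated trials per setting), falls beyond Z > 3.1.**

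| Global shift, analysis | At least one region, A / B | All eight, A / B |
|---|---|---|
| 0%, raw | 0.4% / 0.5% | 0% / 0% |
| -5%, raw | 11% / 5% | 0.5% / 0.1% |
| -10%, raw | 60% / 24% | 10% / 1% |
| -15%, raw | 95% / 60% | 57% / 10% |
| -10%, global CBF as covariate | 1.1% / 0.8% | 0% / 0% |
| -10%, post-minus-pre | 5% / 2% | 0% / 0% |
| +10%, raw | 0% / 0% | 0% / 0% |

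The single-region values (33% and 9%) lie between the at-least-one and all-eight figures, as they should. Adjustment for global CBF restores roughly the error rate expected with no shift. A post-minus-pre contrast does most of the same work when the shift is stable over the session. It would not remove a brain-wide change in the response to water itself.

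**The case against.** The best defence is that the plan may already hold the remedy. Section 9.5.2 speaks of activation during the task and lists resting ASL runs from the same session, which reads naturally as a post-minus-pre comparison. The phrase about quantitative CBF sits in a sentence about resting activity. If that contrast is intended, a stable global shift largely cancels. This stands as a limit on the size of the problem. It does not remove it, because the contrast is nowhere stated and a global change in the water-load response would survive it.

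Several stronger readings are tempting and are not supported:
- A reader might infer that any brain-wide change would pass as diminished activation in all eight regions. Only a fall relative to waitlist fits the hypothesis, and all eight pass together only for large shifts.
- A reader might test regional means at a conventional 5% level and find far higher rates. The plan uses Z > 3.1 clusters, and a cluster-extent requirement could change the rates shown here.
- A reader might conclude that the analysis can never separate regional from global change. If the ASL maps cover the whole brain, a uniform fall would tend to show outside the named regions too; but no rule says how that would be used.
- A reader might add a large loss of precision from differences in flow between children. Each child is scanned at both visits, so a within-child analysis already removes the stable part.

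It is also fair to object that mean grey-matter CBF is measured after treatment and contains the named regions, so adjustment can shrink a true widespread effect. That stands, and it is why the adjusted model should not decide alone.

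**Conclusion.** The omission is real: regional inference from quantitative CBF, a single predicted direction for eight regions, no account of global flow, and no stated contrast. A brain-wide fall in CBF, or in the CBF response to water loading, in ADAPT relative to waitlist could be reported as diminished activation in some or all named regions; a brain-wide rise could mask true regional falls.

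The 24-60% figure for a 10% fall rests on analysis of raw CBF, 20 per arm and the assumed SDs. It drops to 5-11% for a 5% fall. The documents do not show that such a shift will occur. The point bears on how the secondary objective can be interpreted, not on the primary connectivity outcome, and it should be settled before the data are analysed.

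**What to change.** Amend section 9.6 as follows:

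1. State that the Aim 2 contrast is the visit-by-arm difference in the post-minus-pre water-load change in CBF.
2. Compute mean grey-matter CBF from each ASL run and report it by arm, visit and run.
3. Show each Aim 2 contrast twice, for absolute CBF and with the matching mean grey-matter CBF measure (here its post-minus-pre change) as a covariate, with estimates and intervals for both.
4. Describe a change as region-specific only when the adjusted estimate supports it. Where it does not, say that regional and global change could not be separated. Do not treat a non-significant adjusted result as proof of a brain-wide change.

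The cost is SAP wording and one extra model per contrast, on images already to be acquired. The drawback is that the adjusted estimate may understate a true widespread effect, which is the reason for reporting both.

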### Interventions and Duration

In this study, a psychological intervention, Aim to Decrease Anxiety and Pain Treatment (ADAPT), was developed and will integrate mindfulness meditation with cognitive behavioral therapy approaches for managing pain and anxiety to improve patient outcomes. ADAPT is a remotely delivered individual therapy with caregiver involvement that consists of 2 video-recorded sessions with an interventionist (60 minutes) once per week for the first two weeks, followed by 4 weeks of self-paced web modules (45 minutes per week) in conjunction with interventionist support (15 minutes per week). Of note, participants will complete the ADAPT program through a HIPAA compliant video platform (Zoom) or over phone calls as an alternate delivery method. Zoom sessions will be video recorded to measure interventionist adherence and for training purposes. The duration of ADAPT is 6 weeks, although up to eight weeks will be permitted to account for scheduling conflicts and participant illness. Preliminary testing has shown that ADAPT successfully reduces pain and anxiety over time.

Participants randomized to ADAPT will be actively involved in the study for a ~10 week period (from screening to post assessment). Those who are randomized to the waitlist control and then opt to receive ADAPT afterwards will be involved for ~16 weeks.

